9.4. Data Sources

Data will be participant- and clinician-reported. The registries will collect data from participants with SMA who are enrolled in the ISMAR-US, UK Adult SMA-REACH, and SMArtCARE SMA registries if they become pregnant within the relevant exposure window for nusinersen. Participants will be consented and enrolled through the registries (see information on informed consent in Section 10.2). The registries will also collect data from the participants' HCPs (e.g., obstetrician, pediatrician) and electronic medical records. In addition, previously collected data for the participant from the registry will be used. Biogen will receive data in the form of aggregate summary tables.

It is expected that participants and HCPs will be contacted according to the details outlined in Section 9.3.2 and the recommended study contact schedule (Section 16). While contacts for this study are not mandated, registries will inform participants and HCPs of the expected contact schedule and make every effort to ensure data are entered for each expected contact.

If the sample size allows for comparative analysis, reporting rates from the study will be compared with available background rates for pregnancy outcomes in women without SMA who were not exposed to nusinersen using the MACDP and EUROCAT general population databases, as appropriate (see Section 9.7.3.2).

9.5. Study Size

The goal of the research initiative is to enroll as many participants with SMA who receive nusinersen during pregnancy (or within the relevant exposure window) as possible. Based on the number of individuals of childbearing potential currently enrolled in the registries or who come of childbearing age over the duration of the study and the number of incident pregnancies observed in the registries to date, the estimated enrollment number over the 10-year study period is 20 pregnancies.

As of August 2024, the UK Adult SMA-REACH registry has approximately 285 genetically confirmed SMA patients with 72 using nusinersen [Walker 2024]. In the SMArtCARE registry, as of May 2021, there were 965 SMA patients enrolled. This includes 147 women of childbearing age, of whom 117 have been treated with nusinersen.

While enrollment may slow over time, some increase in new patients is expected in all of the registries. In addition to newly enrolled patients, younger patients are expected to reach childbearing age over the next few years. Together, these factors should lead to an increase in individuals of childbearing age in the registries, which will increase the likelihood of capturing incident pregnancies.

9.6. Data Management

Data management and statistical software to be used in the study, including procedures for data collection, retrieval, and preparation, are outlined in the statistical analysis plan. Data collection and management will be handled by the registries.

9.7. Data Analysis

9.7.1. General Discussion of the Analysis

All participants will be reviewed based on earliest exposure within the relevant nusinersen exposure window.

The registries and Biogen Epidemiology and Global Safety will carefully review each pregnancy outcome and the frequency of adverse pregnancy outcomes. For this study, gestational weeks are calculated beginning from the first day of the participant's LMP. If the date of LMP is not available, the EDD may be used. If the gestational week is

inconsistent with the exposure dates and/or the dates of outcomes (outside of 1 week for the first trimester, outside of 2 weeks for the second and third trimesters) and a corrected EDD (i.e., generally by ultrasound) is available, the corrected EDD is used for gestational week calculations.

Descriptive analyses will be performed to analyze the risks of MCMs, spontaneous abortions, SGA births, and abnormal postnatal growth and development.

Statistical analyses may be performed to examine potential increases in risks of MCMs, spontaneous abortions, SGA births, and abnormal postnatal growth and development as compared with the expected background prevalence. The prevalence and 95% CIs for study participants may be calculated to assess the presence of any excessive risk associated with nusinersen exposure.

All analyses will be conducted on an overall basis as well as grouped by the earliest trimester of exposure. For MCMs, analyses will be conducted only for participants who have exposure in the first trimester. In the absence of treatment initiation during the second and third trimester of pregnancy, the subgroups with small sample sizes may be collapsed as needed. Other adverse pregnancy outcomes will be examined similarly as the sample size permits.

A periodic review of the study will be performed by monitoring reports of adverse pregnancy outcomes for nusinersen (see Section 9.7.4).

9.7.2. Analysis Population

The primary population for analysis will be prospective reports of pregnancies exposed to nusinersen. Participants who enroll after the outcome of pregnancy is known will be enrolled as retrospective cases but will not be included in the primary analysis.

Analyses of MCMs, spontaneous abortions, SGA births, and abnormal postnatal growth and development may be conducted on the following subgroups:

- Participants who enroll prior to prenatal testing as well as participants who enroll after prenatal testing
- Participants who enroll after prenatal diagnosis showing any major structural defects
- Participants with similar characteristics to comparator data (e.g., MACDP, EUROCAT), if applicable

9.7.3. Methods of Analysis

Each pregnancy outcome will be classified into the categories described in Section 9.3 and will be collected and reported separately. Data will be presented in aggregate tables in the interim and final reports.

All analyses will be conducted on an overall basis, as well as stratified by earliest trimester of exposure. For MCMs, analyses will be conducted only for participants who have exposure in the first trimester. The prevalence and 95% CIs of spontaneous abortions, MCMs, SGA births, and abnormal postnatal growth and development will be CONFIDENTIAL

The information contained herein may not be used, disclosed, or published without the written consent of Biogen MA Inc.

calculated. Other negative pregnancy outcomes will be similarly examined as the sample size permits. Infants with minor malformations, chromosomal abnormalities, genetic syndromes, positional defects, and prematurity-related defects will be excluded from the primary analyses related to MCM prevalence; these outcomes will be reported in the interim and final reports. Details of the analysis will be provided in the statistical analysis plan.

If sufficient enrollment numbers are obtained, analyses will also be stratified according to maternal age, gestational age at enrollment, medical condition at time of pregnancy that may affect pregnancy outcome (including but not limited to respiratory, neuropsychiatric, metabolic, cardiovascular, infectious, hematological disease or impairment), and other important risk factors (e.g., concurrent medications and substance use).

Demographic information, clinical characteristics, and other potential factors that may affect pregnancy outcome will be described.

The actual date of delivery (not the EDD) will be used in all analyses. EDD will only be used to schedule outreach to HCPs to ascertain the outcome of an expected birth.

For each interim analysis, pregnancy and infant outcomes will be analyzed cumulatively from the beginning of the study.

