7.1.2. Clinical Experience With Nusinersen in Pregnant Women

There are no adequate data on the developmental risk associated with the use of nusinersen in pregnant individuals. There are no data from clinical studies on the use of nusinersen during pregnancy in humans, and there are limited data on the use of nusinersen during pregnancy from the postmarketing setting.

There are no data on the presence of nusinersen in human milk, the effects on the breastfed infant, or the effects of the treatment on milk production. However, based on the available nonclinical data, the risk of nusinersen exposure through breast milk to breastfeeding children is low.

In the US general population, the estimated background risk of major birth defects and miscarriage in clinically recognized pregnancies is 2% to 4% and 15% to 20%, respectively. The background risk of major birth defects and miscarriage for the indicated population is unknown.

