9.2.2.1. Inclusion Criteria

- 1. Individual who is currently pregnant (or was pregnant during the relevant exposure window; see inclusion criterion 4) and enrolled in the ISMAR-US, UK Adult SMA-REACH, or the Germany, Austria, or Switzerland network of the SMArtCARE registry.
- 2. Ability of the participant and/or their legally authorized representative (e.g., parent, spouse, or legal guardian), as appropriate and where allowed by local regulations, to understand the purpose and risks of the study, to provide informed consent, and to authorize the use of confidential health information in accordance with national and local privacy regulations.
- 3. Genetic documentation of 5q SMA.
- 4. Documentation that the participant was exposed to nusinersen up to 14 months prior to the first day of their LMP before conception, 14.5 months before conception, and/or at any time during their pregnancy. If exact exposure dates are CONFIDENTIAL

unknown, the reporter must be able to estimate either the months of exposure during pregnancy or the trimester of exposure.

5. Agreement to release medical information, thereby permitting the registry to contact the participant's HCPs and the pediatric HCP for medical information.

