9.3.1.1.2. Spontaneous Abortion

Spontaneous abortion is defined as any loss of a fetus due to natural causes at < 20 weeks of gestation [FDA 2002, 2019]. If available, data from gross or pathologic examination of the abortus or fetus will be evaluated for structural or chromosomal defects.

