9.7.3.1.1. Spontaneous Abortion

The prevalence of spontaneous abortion reported to the study will be calculated by dividing the number of fetal losses occurring at < 20 weeks of gestational age by the total number of pregnancies. If sufficient enrollment numbers are obtained, analysis of spontaneous abortions may be stratified by earliest trimester of exposure, gestational age at enrollment, maternal age, medical condition that may result in negative pregnancy outcomes, and other maternal risk factors, as appropriate. Sensitivity analyses may be performed for spontaneous abortions and may be stratified by each trimester, along with these factors, when the sample size allows.

The 95% CIs for spontaneous abortion rates will be calculated based on the binomial distribution. If sufficient enrollment numbers are obtained, spontaneous abortion rates may also be presented in subgroups by the earliest trimester of exposure, gestational age at enrollment, maternal age, medical condition, and other maternal risk factors at enrollment, as appropriate.

In addition, time to spontaneous abortion will be analyzed using the Kaplan-Meier method.

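### Splitting spontaneous abortion by earliest trimester of exposure biases the later strata downward whatever the drug does, because a pregnancy must survive to a dose to enter that dose's stratum

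*Protocol*

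**What the plan says.** Protocol 9.7.3 sets a general rule: "All analyses will be conducted on an overall basis, as well as stratified by earliest trimester of exposure". Section 9.7.1 says the same. The only outcome with its own exposure-timing rule is major congenital malformation, which is analysed in first-trimester exposures only.

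For spontaneous abortion, 9.7.3.1.1 repeats the split conditionally: "If sufficient enrollment numbers are obtained, analysis of spontaneous abortions may be stratified by earliest trimester of exposure". The rate itself is obtained by "dividing the number of fetal losses occurring at < 20 weeks of gestational age by the total number of pregnancies".

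Three definitions matter here:
- Event (9.3.1.1.2): "Spontaneous abortion is defined as any loss of a fetus due to natural causes at < 20 weeks of gestation".
- Clock (9.7.1): "gestational weeks are calculated beginning from the first day of the participant's LMP".
- Qualifying exposure (9.2.2.1): up to 14 months before the LMP, "and/or at any time during their pregnancy".

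Section 9.7.1 also says participants are reviewed by earliest exposure within that window. It allows small subgroups to be collapsed if no treatment starts in the second or third trimester. No preconception category is named.

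**The concern.** The strata are defined by something that happens during follow-up. A pregnancy lost at 9 weeks cannot receive a first dose at 15 or 30 weeks, so it can appear only in the first-trimester group or in a group with no dose in pregnancy. Gestational time before the qualifying dose is event-free by construction in every later stratum. This is immortal time.

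The table would then show loss rates falling with later exposure even if nusinersen does nothing. A reader of the interim reports, which are cumulative and at least annual, could take early exposure to be harmful or late dosing to be protective. Neither reading would have support.

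The protocol's existing measures address something else. Stratifying by gestational age at enrollment (9.7.3, 9.7.3.1.1, 9.9) deals with late entry to the study, not late exposure. A woman enrolled at week 6 on a preconception dose, with her first dose in pregnancy at week 15, still has weeks 6 to 15 guaranteed free of loss if she is placed in the second-trimester stratum. The Kaplan-Meier analysis is stated without any handling of exposure time. Section 9.9 does not mention this bias.

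**Working it through.** The protocol gives no stratum-specific rate to reproduce. The check asks what the stated estimator returns for a drug with no effect.

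**Inputs from the protocol**
- Background miscarriage risk p = 15% to 20% (7.1.2: "the estimated background risk of major birth defects and miscarriage in clinically recognized pregnancies is 2% to 4% and 15% to 20%, respectively").
- Event window: below 20 weeks from the LMP.
- Estimated enrollment: 20 pregnancies (9.5).

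**Assumptions not in the protocol**
- The second trimester starts at week 14 and the third at week 28.
- A share e = 70% to 90% of recognised losses falls before week 14.
- For steps 3 to 5, losses are spread evenly over weeks 5 to 14 and over weeks 14 to 20.

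**Step 1: third-trimester stratum.** Everyone in it has passed week 28, and the event cannot occur at or after week 20. The rate is 0% by definition. This holds for any third-trimester cut-point at or after week 20.

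**Step 2: upper limit for the second-trimester stratum.** Suppose every pregnancy in it were dosed exactly at week 14. The risk among those still pregnant at week 14 is p(1 − e)/(1 − pe).

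| p | e | p(1 − e) | 1 − pe | Risk |
|---|---|---|---|---|
| 0.15 | 0.9 | 0.015 | 0.865 | 1.7% |
| 0.15 | 0.7 | 0.045 | 0.895 | 5.0% |
| 0.20 | 0.9 | 0.020 | 0.820 | 2.4% |
| 0.20 | 0.7 | 0.060 | 0.860 | 7.0% |

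So at most 1.7% to 7.0%, against a true risk of 15% to 20%.

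**Step 3: first doses spread evenly within each trimester.** Stratum risk = 1 − S(20)/mean of S(dose time), where S is the probability of still being pregnant. Over the same ranges this gives 11% to 16% in the first-trimester stratum, 0.4% to 1.6% in the second and 0% in the third.

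**Step 4: maintenance dosing, strata set by the first dose in pregnancy.** Assume p = 17.5% and a first in-pregnancy dose spread evenly over 17.4 weeks (an assumed interval of about 4 months). Then S(20) = 0.825.
- First-trimester stratum: mean S is 0.961 for e = 0.7 and 0.949 for e = 0.9, so the risk is 1 − 0.825/0.961 = 14.1% and 1 − 0.825/0.949 = 13.1%.
- Second-trimester stratum (doses in weeks 14 to 17.4): mean S is 0.8626 and 0.8375, so the risk is 4.4% and 1.5%.
- Under this schedule no pregnancy enters the third-trimester stratum. The 0% there comes from step 1 only.

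**Step 5: women with no dose in pregnancy, same setting.** If everyone stays on schedule, the only pregnancies without a dose are those lost before it, so the rate is 100%. If half stop dosing at week 6 (assumed), simulation gives about 24% to 26%. This group is biased upward.

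**Step 6: late enrollment.** Repeating step 3 with enrollment no earlier than week 8 leaves a first-to-second ratio of about 9 to 24. With week 12 it is about 6 to 13. Late entry does not remove the gradient.

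**Step 7: what 20 pregnancies can show.** Expected losses are 20 × 0.15 = 3 to 20 × 0.20 = 4. An illustrative result is 3/15 (20%, exact 95% CI 4% to 48%) against 0/5 (0%, CI 0% to 52%), Fisher p = 0.54.

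**The case against.** **Earliest exposure may include doses before the LMP.** Section 9.7.1 ties it to a window that opens 14 months before the LMP. On that reading, women on maintenance dosing are classified before conception. Only those first exposed in the second or third trimester are affected, and 9.7.1 foresees that there may be none. This stands as a limit on scope. It does not dispose of the point, because the strata are called trimesters, no preconception category is named, and the collapsing clause does not apply when the later strata are populated, which is when the bias appears.

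**A reader might infer that early exposure will show an excess over the expected rate.** The figures do not support that. With no drug effect the first-trimester stratum (11% to 16%) is not above the 15% to 20% background; the later strata are pushed down. The comparison in 9.7.3.2 is with external rates, and this route does not inflate it for that stratum. Only a group with no dose in pregnancy would exceed background, and the protocol names no such group.

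**A reader might also infer a demonstrable false signal.** At this size there is none. No test between strata is planned and the intervals overlap widely. In step 4 about 4 of 20 first doses fall in weeks 14 to 17.4. Seeing 0/4 has probability 0.825^4 = 46% with no bias at all, and 0.97^4 = 89% at a 3% risk.

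**The split may never be produced.** Section 9.7.3.1.1 says *may*, subject to enrollment. But 9.7.1 and 9.7.3 say *will*, so the text is in conflict.

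**The overall rate might be thought equally distorted.** A pregnancy that qualifies only through a dose after week 20 does sit in the denominator without being able to miscarry while exposed. It would need no dose from 14 months before the LMP through week 20. The documents give no basis for supposing that is common.

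**Conclusion.** The point holds. As written, the plan calls for a breakdown of spontaneous abortion in which the third-trimester rate is 0% by definition and the second-trimester rate is at most about 1.7% to 7.0% for a drug with no effect. That upper limit rests on the protocol's background risk, an assumed week-14 boundary and an assumed 70% to 90% of losses before it. The size of the first-to-second contrast is less certain: roughly 3- to 9-fold under step 4 and 10- to 30-fold under step 3, depending on assumed dose timing.

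Its reach depends on an undefined term. If strata use the first dose in pregnancy, all users are affected and any group without such a dose is biased upward. If doses before the LMP count, only women first exposed in the second or third trimester are affected.

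With about 20 pregnancies the consequence is a misleading pattern in descriptive point estimates. It should be corrected, but it does not undermine the overall loss rate.

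**What to change.** In 9.7.1, 9.7.3 and 9.7.3.1.1:
- Exempt spontaneous abortion from stratification by earliest trimester, as malformations already have their own rule, and reconcile *will* with *may*.
- Limit its denominator to pregnancies exposed before conception or before 20 weeks, and before the outcome.
- If a split by exposure timing is wanted, use one fixed at the LMP, such as time since the last dose before it. Alternatively, count risk only from the later of first exposure and enrollment.
- State whether earliest exposure includes doses before the LMP, and name a preconception category.
- Apply the same caution to premature birth: a 27-week delivery cannot enter a stratum that begins at week 28.

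Dose dates, LMP and outcome information are already collected (9.3.2). The cost is protocol and analysis-plan wording plus minor table changes by the registries, since the sponsor receives only aggregate tables (9.4). A full model with time-dependent exposure is optional; with 3 to 4 expected losses it would add little.

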8.2.1. Pregnancy and Infant Outcomes

Pregnancy outcomes include pregnancy loss (pregnancy termination, spontaneous abortion, and fetal death [stillbirth]) and live birth (premature birth and full-term birth). Within each of these categories, the fetus or infant will be evaluated as to the presence or absence of anomalies or other fetal effects.

Pregnancy Loss

- Pregnancy termination (any induced or voluntary fetal loss during pregnancy)
- Spontaneous abortion (< 20 weeks of gestation)
- Fetal death, including stillbirth (fetuses born dead at ≥ 20 weeks of gestation or fetuses born dead at ≥ 350 g if gestational age is unknown), which is further classified as follows:
 - Early fetal loss (fetal death occurring at ≥ 20 weeks but ≤ 28 weeks of gestation)
 - Late fetal loss (occurring at \geq 28 weeks of gestation)

Live Birth

• Premature birth (delivered < 37 weeks)

CONFIDENTIAL

• Full term birth (delivered \geq 37 weeks)

Infant deaths up to 52 weeks of age, as defined in Section 9.3, will be reported among live births.

Major Congenital Malformations

- Interchangeably referred to as congenital malformations, congenital anomalies, and birth defects.
- Abnormalities in structural development that are medically or cosmetically significant, are present at birth, and persist in postnatal life unless or until repaired, as evaluated by independent advisors.

In addition, SGA births, abnormal postnatal growth and development (i.e., social/emotional, language/communication, neurocognitive, movement/physical development milestones) up to 2 years of age, ectopic pregnancies, and molar pregnancies will be reported for each pregnancy outcome (see Section 9.3). Given that SMA is a genetic condition, it is possible that babies born to an individual with SMA will also have SMA. Therefore, the diagnosis of SMA in infants will also be collected.

Maternal death during pregnancy, labor, delivery, or up to 12 weeks after delivery will be reported. Infant deaths occurring up to 52 weeks of age will also be reported.

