9.3.1. Variable Definitions

9.3.1.1. Pregnancy Loss

9.3.1.1.1. Pregnancy Termination

A pregnancy termination is defined as any induced or voluntary fetal loss during pregnancy. If possible, the reason for pregnancy termination (e.g., related to SMA, nusinersen, other) should be collected. If available, data from gross or pathologic examination of the abortus or fetus will be evaluated for structural or chromosomal defects.

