9.3.1.4. Major Congenital Malformations

MCMs (interchangeably referred to as congenital malformations, congenital anomalies, and birth defects) are abnormalities in structural development that are medically or cosmetically significant, are present at birth, and persist in postnatal life unless or until repaired, as evaluated by independent advisors (see Section 9.7.5).

All potential MCMs, including minor anomalies, from all countries in which the study will be conducted will be evaluated by a qualified independent teratologist or other appropriate MCM evaluator using all available medical records. The classification of all potential MCMs used in analyses will be based upon the teratologist's adjudication. The exact grouping of MCMs (e.g., major versus minor defects) will vary by analysis in order to mirror the classification systems used in the selected external comparator groups. Minor malformations, chromosomal abnormalities, genetic syndromes, positional defects, and prematurity-related defects will be excluded from major malformations in the primary analyses.

The major birth defect classification system used in this study will align with the choice of external comparator. For example, comparisons of the nusinersen-exposed participants to EUROCAT estimates will be consistent with the EUROCAT classification schema and the EMA pregnancy guidance. Similarly, the MACDP classification will be used when comparing to the MACDP external comparator. All cases will be reviewed based on earliest exposure to nusinersen.

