9.7.3.1.2. Major Congenital Malformations

The prevalence of MCMs (referred to as birth defects in EUROCAT) reported to the study will be calculated using EUROCAT conventions (http://www.eurocat-network.eu/accessprevalencedata/interpretationguide/calculationofprevalencerates). The prevalence of 1 or more MCMs in addition to the prevalence of specific MCMs will be calculated as follows:

Total Prevalence of Teratologist-Confirmed MCMs = Number of Teratologist-Confirmed Cases / Number of Births (Live and Still)

Other formulas for prevalence may be used to calculate estimates for comparisons to other background rates from other sources.

The analysis of MCM outcomes will be conducted only for participants who have exposure during the first trimester, adjusting for maternal age, medical condition, and other maternal risk factors at enrollment, as appropriate. Sensitivity analyses may be performed for MCMs and may be stratified by each trimester, along with the above factors, when the sample size allows.

The 95% CIs for MCM rates will be calculated based on the binomial distribution.

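### Sections 9.3.1.4 and 9.7.3 contradict each other on whether listed defects or the infants who have them are excluded from the primary MCM prevalence; read literally, 9.7.3 can remove a true case

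*Protocol*

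**What the plan says.** Two sections of the Protocol apply the same list of anomalies to the primary MCM analysis.

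- Section 9.3.1.4, the variable definition: "Minor malformations, chromosomal abnormalities, genetic syndromes, positional defects, and prematurity-related defects will be excluded from major malformations in the primary analyses". The unit is the defect.
- Section 9.7.3, the analysis methods: "Infants with minor malformations, chromosomal abnormalities, genetic syndromes, positional defects, and prematurity-related defects will be excluded from the primary analyses related to MCM prevalence". The unit is the infant. The sentence goes on to say that these outcomes will appear in the interim and final reports.

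Section 9.7.3.1.2 says the prevalence "will be calculated using EUROCAT conventions", cited by link, and gives the formula "Number of Teratologist-Confirmed Cases / Number of Births (Live and Still)". On the interval it says: "The 95% CIs for MCM rates will be calculated based on the binomial distribution".

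On which pregnancies can supply a case, section 9.3.1.1.1 (terminations) says that, if available, "data from gross or pathologic examination of the abortus or fetus will be evaluated for structural or chromosomal defects". Section 9.3.1.1.2 says the same for spontaneous abortions. Section 8.2.1, after listing losses and live births, adds: "Within each of these categories, the fetus or infant will be evaluated as to the presence or absence of anomalies or other fetal effects". The MCM definition in 9.3.1.4, however, requires the abnormality to exist at birth.

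**The concern.** A rule on defects affects only the numerator. A rule on infants also changes the denominator, and it can delete a case that qualifies on other grounds. An analyst cannot follow both.

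Co-occurrence is plausible here. Section 9.3.1.4 sends minor anomalies to the teratologist along with potential MCMs, so they will be recorded. The Protocol also expects that some infants may have SMA (sections 7.2.3 and 8.2.1) and does not say whether SMA is a genetic syndrome for this rule. If it is, the infant-level wording would remove every affected infant, whatever other malformation is present.

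The study expects 20 pregnancies (section 9.5), so the MCM result will probably rest on no case or one. Section 9.7.3.2 bases the external comparison on point estimates and 95% CIs, and reports are cumulative and at least annual (section 9.7.4). If the rule stays unsettled, the choice between readings could be made once a case is known.

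The second gap is similar. Fetuses from terminations and losses are evaluated for defects, the formula does not limit cases to births, and the denominator holds births only. The definition points to a births-only case set but does not say so.

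**Working it through.** **No stated figure to reproduce.** The 20 pregnancies are a feasibility count, and the Protocol gives no expected MCM prevalence or CI width.

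**Inputs**
- 20 pregnancies (section 9.5).
- Background risks of 15-20% for miscarriage and 2-4% for major defects (section 7.1.2, US general population).
- Births, as an assumption: 20 x 0.85 = 17 to 20 x 0.80 = 16. This is roughly an upper bound, because MCM analyses are limited to first-trimester exposure (section 9.7.1). Values of 10 and 20 births are shown as a range.
- The case mixes below are illustrations, not forecasts.

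**Interval.** Exact binomial (Clopper-Pearson), x cases in n: lower limit = Beta(0.025; x, n-x+1), upper limit = Beta(0.975; x+1, n-x). For x = 0 the upper limit is 1 - 0.025^(1/n); for n = 16 this is 20.6%.

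**How many cases to expect.** In 16 births:
- P(at least one MCM) = 1 - 0.98^16 = 28% at a 2% risk, and 1 - 0.96^16 = 48% at 4%.
- P(none or one) = 0.98^16 + 16 x 0.02 x 0.98^15 = 0.724 + 0.236 = 96% at 2%, and 0.520 + 0.347 = 87% at 4%.

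**Unit of exclusion.** Let n births include c infants with a qualifying MCM. Of these, k also have a listed finding. A further m infants have only listed findings. Section 9.3.1.4 gives c/n; section 9.7.3 gives (c-k)/(n-k-m).

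| Case mix | 9.3.1.4: defects out | 9.7.3: infants out |
|---|---|---|
| 20 births, c=1, k=1, m=0 | 1/20 = 5.0% (0.1-24.9%) | 0/19 = 0% (0-17.6%) |
| 17 births, c=1, k=1, m=0 | 1/17 = 5.9% (0.1-28.7%) | 0/16 = 0% (0-20.6%) |
| 16 births, c=1, k=1, m=0 | 1/16 = 6.3% (0.2-30.2%) | 0/15 = 0% (0-21.8%) |
| 10 births, c=1, k=1, m=0 | 1/10 = 10.0% (0.3-44.5%) | 0/9 = 0% (0-33.6%) |
| 17 births, c=1, k=0, m=3 | 1/17 = 5.9% (0.1-28.7%) | 1/14 = 7.1% (0.2-33.9%) |

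The error can run either way: down when the case itself has a listed finding, up when only non-cases do.

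In expectation, take a true prevalence of 3% and assume that 10% of non-case infants and a share q of case infants have a listed finding. The infant-level estimate tends to 0.03(1-q) / [0.03(1-q) + 0.97 x 0.9]. This is 3.0% at q = 0.1, 2.3% at q = 0.3 and 1.7% at q = 0.5. The Protocol gives no value for q.

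**Cases outside the denominator.** Suppose one MCM in a birth and one in a termination, with no other termination.

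| Births | Births only | Formula with the termination case counted | Termination in both parts |
|---|---|---|---|
| 17 | 1/17 = 5.9% (0.1-28.7%) | 2/17 = 11.8% (1.5-36.4%) | 2/18 = 11.1% (1.4-34.7%) |
| 10 | 1/10 = 10.0% (0.3-44.5%) | 2/10 = 20.0% (2.5-55.6%) | 2/11 = 18.2% (2.3-51.8%) |

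The large step is whether the termination case counts at all (5.9% to 11.8%). Matching the denominator then changes little (11.8% to 11.1%).

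**The case against.** The best defence is that the defect-level rule is what the sponsor means. Section 9.7.3 opens by sending outcomes to the categories of section 9.3, where that rule sits. Section 9.7.3.1.2 counts one or more teratologist-confirmed MCMs, which makes an infant with a heart defect and a minor anomaly a natural case. The 9.7.3 sentence ends by calling the excluded items outcomes and promising to report them. Analysis detail is left to the statistical analysis plan, which is not shown, and an independent teratologist and an advisory board stand between the data and the classification.

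Much of this is fair, and it shows which rule is probably intended. It does not remove the contradiction. A statistical analysis plan cannot comply with both sentences. Reporting an excluded outcome elsewhere does not put it back into the prevalence. Adjudication decides what a defect is, not whether its carrier is counted.

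It also stands that the analysis is descriptive and the comparison is made only where sample size permits. Every interval shown above contains the 2-4% background range, so no conclusion reverses in these examples.

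Two stronger readings are tempting, and the Protocol does not support them:

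- A reader might infer that the binomial CI is invalid. No sentence says that termination or loss cases enter the numerator, and the definition suggests they do not. With births in both parts the binomial interval is valid. The infant-level exclusion can bias the estimate but does not itself break the binomial model. What the EUROCAT convention counts cannot be checked from the Protocol.
- A reader might infer that true cases vanish from the study. They would leave the primary prevalence, not the reports.

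**Conclusion.** The contradiction on the unit of exclusion holds. Section 9.7.3 as written states a rule that differs from the definition in 9.3.1.4 and can give a wrong primary MCM prevalence. With 16-17 births, one infant with both an MCM and a listed finding takes the estimate from about 6% to 0%. This rests on the assumed miscarriage share and on such an infant occurring; the Protocol gives no co-occurrence rate.

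The termination point holds only as an open specification. The Protocol should say which cases count. The binomial interval is unsuitable only if non-birth cases are counted, and in the 17-birth example the upper limit then differs by 36.4 - 34.7 = 1.7 percentage points from a matched denominator.

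This is a correction of stated wording, not a flaw in the design.

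**What to change.** 1. In section 9.7.3, replace the infant-level exclusion with: *These defects are not counted as MCMs; an infant or fetus who also has a qualifying MCM remains a case, and all births remain in the denominator.* This matches section 9.3.1.4. If the sponsor wants malformations explained by a chromosomal or genetic syndrome not to qualify, say so as a numerator rule, and say whether SMA falls under it.
2. In section 9.7.3.1.2, state whether MCMs found in terminations and losses are cases, and make the definition in 9.3.1.4 agree. Use a births-only numerator over live plus still births for the binomial CI. If termination or loss cases are also counted, report that estimate separately, with a matching denominator or an interval suited to a ratio.

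The cost is a few sentences, and one more table row if the second estimate is reported. No new data are needed. The wording should be settled before MCM cases are analysed.
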